6.1.2 Planned Maintenance Treatment

Patients are randomised to one of five treatment groups (Placebo, BI 456906 0.6 mg, BI 456906 2.4 mg, BI 456906 3.6 mg, BI 456906 4.8 mg). These are the planned maintenance treatments (weekly doses).

6.1.3 Actual Maintenance Treatment

According to the rules for escalating and adjusting the BI 456906 dose given in the CTP, it is envisaged that some patients may not receive the planned maintenance treatment according to the randomised treatment group, whilst nevertheless remaining on treatment.

Actual maintenance treatment will therefore be defined for analysis as follows:

- If the actual dose at the start of the maintenance period is known to be less than the planned maintenance dose to which the patient was randomised, then actual maintenance treatment will be defined as this dose at the start of the maintenance period (which is expected to be one of the lower planned maintenance doses).
- If the patient was known to have discontinued treatment during the dose escalation period, actual maintenance treatment will be defined as the next planned maintenance dose up from the last dose which was taken prior to the dose at the time of discontinuation. This is specified in the table below, for all dosing possibilities planned in the CTP. The same rule will be applied irrespective of the reason for discontinuing treatment during the dose escalation period.

Table 6.1.3: 1 Definition of actual maintenance treatment for patients randomised to active BI 456906 maintenance treatment who discontinued treatment during the dose escalation period

Dose at discontinuation / Previous dose	Actual maintenance treatment
0.3 mg / NA	0.6 mg
0.6 mg / 0.3 mg	0.6 mg
0.9 mg / 0.6 mg	2.4 mg
1.2 mg / 0.9 mg	2.4 mg
1.8 mg / 1.2 mg	2.4 mg
2.4 mg / 1.8 mg	2.4 mg
3.0 mg / 2.4 mg	3.6 mg
3.3 mg / 2.4 mg	3.6 mg
3.6 mg / 3.0 mg	3.6 mg
4.2 mg / 3.3 mg	3.6 mg
4.8 mg / 4.2 mg	4.8 mg

- In all other cases, actual maintenance treatment will be defined equal to planned maintenance treatment.
- All patients randomised to placebo maintenance treatment will be assigned to placebo for actual maintenance treatment.

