7. PLANNED ANALYSIS

Descriptive statistics for continuous variables will generally be N (number of patients with non-missing values), arithmetic mean, standard deviation (SD), minimum, Q1 (lower quartile), median, Q3 (upper quartile) and maximum. In general, means, medians, other quartiles and SDs will be presented to one more decimal place than the raw data. Minimums and maximums will be presented to the same number of decimal places as the raw data.

For BI 456906 plasma concentrations, CV (arithmetic coefficient of variation), gMean (geometric mean) and gCV (geometric coefficient of variation) will also be presented. The data format for descriptive statistics of concentrations will be identical with the data format of the respective concentrations.

Tabulations of frequencies for categorical data will include all possible non-missing categories unless otherwise specified (e.g. AE terms), and will display the number of patients in a category as well as the percentage (%) relative to the respective treatment group. Percentages will be rounded to one decimal place. A missing category will be displayed only if there are actually missing values. Percentages will be based on all patients in the respective patient set whether they have non-missing values or not.

Disposition

The disposition of patients will be displayed. This table will present the number of patients enrolled, randomised and treated. The number treated will be further presented separating the dose escalation and maintenance periods. Planned maintenance treatment (see [Section 6.1.2](#)) will be used for this table.

The number of patients who completed or who prematurely discontinued study treatment will be summarised, along with the categorization of the primary reason for treatment discontinuation. The number of patients and reasons for prematurely discontinuing treatment will also be displayed separately for the dose escalation and maintenance periods.

The number of patients who completed or who prematurely withdrew from the study will be summarised, along with the categorization of the primary reason for study withdrawal.

Where shown on the disposition table, the percentages will be of the number of patients treated in each treatment group.

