7.8 SAFETY ANALYSIS

All safety analyses will be performed on the TS, using actual maintenance treatment, and including only on-treatment data (unless otherwise specified in [Section 7.8.1](#)), regardless of whether early treatment discontinuation was COVID-19 related.

Selected AE summaries will also be presented on the TS using planned maintenance treatment. Where this is also planned, it is clearly specified.

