7.8.1 Adverse Events

The analyses of adverse events will be descriptive in nature. All analyses of AEs will be based on the number of patients with AEs and not on the number of AEs.

The analysis of adverse events will be based on the concept of treatment emergent adverse events. AEs will be considered “on-treatment” if the AE start date meets the 28-day REP criterion (see [Section 6.1.6](#)). AEs occurring prior to the start of treatment will be assigned to “screening”. AEs occurring more than 28 days after the last dose of study treatment will be assigned to “follow-up”. Unless otherwise specified, on-treatment AEs will be pooled across dose escalation and maintenance periods. It should also be noted that the protocol encourages continued study participation for patients who have discontinued treatment early. It is therefore expected that for some patients there will be off-treatment data captured during the planned treatment period, which will make the “follow-up” period included in AE summaries longer than the 4-week definition of scheduled “follow-up” used in the protocol, perhaps in some cases considerably longer than this.

An overall summary of adverse events will be presented for all treated patients. This summary will show the number and percent of patients with any AE, any investigator defined drug-related AE, any AE leading to the discontinuation of study medication, any AESI (as determined by the investigator), any serious AE (including reason for serious (death, life-threatening, disability/permanent damage, required or prolonged hospitalization, congenital anomaly/birth defect and other medically important events)), and any drug-related serious AE. The overall summary will be presented:

- Using actual maintenance treatment, with the treatment period pooled across, and split into, dose escalation and maintenance periods, respectively.
- Using planned maintenance treatment, with the treatment period pooled across dose escalation and maintenance periods only.

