AEs will be coded using the version of the MedDRA coding dictionary in force at final DBL. The frequency of patients with all AEs will be summarised by treatment, primary system organ class (SOC) and preferred term (PT). A patient with multiple on-treatment occurrences of the same preferred term meeting the criteria for inclusion in the table will be counted only once in these tabulations. SOC's will be sorted by descending overall frequency; PT's will be sorted by descending overall frequency (within SOC). The summary of all AEs will be presented:

- Using actual maintenance treatment, with the treatment period pooled across, and split into, dose escalation and maintenance periods, respectively.

- Using planned maintenance treatment, with the treatment period pooled across dose escalation and maintenance periods only.

The AE summary by primary SOC and PT will also be repeated for each of the following, using actual maintenance treatment with the treatment period pooled across dose escalation and maintenance periods, only:

- AEs leading to treatment discontinuation
- Serious AEs
- Investigator-defined drug-related AEs
- Drug-related serious AEs.

An additional table will present the frequency of patients with AEs by worst intensity (mild, moderate, severe) and by primary SOC and PT. Where no events meet the criteria for inclusion in one of these tables, the table will be shown as indicating no events of that intensity have occurred.

The following tables will be produced by baseline body weight subgroup (< 100 / ≥ 100 kg):

- Overall AE summary
- Summary of all AEs by primary SOC and PT
- Summary of AEs leading to treatment discontinuation by primary SOC and PT.

For disclosure of AE data on ClinicalTrials.gov, the frequency of patients with non-serious AEs occurring with an incidence of greater than 5% (PT occurring in more than 5% of treated patients in one or more treatment groups) will be summarised by treatment, primary SOC and PT. The frequency of patients with serious AEs and drug related serious AEs will also be summarised respectively.

For disclosure of AE data in the EudraCT register, the frequency of patients with AEs, the frequency of patients with non-serious AEs with an incidence of greater than 5% (as above) and the frequency of patients with serious AEs will be summarised. Furthermore, the total number of treated patients by country and by age group will be summarised.

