An exposure-adjusted summary of all AEs by primary SOC and PT will also be produced. For this purpose, the time at risk will be defined for specific AEs as follows:

- For patients with no events, the time at risk is the number of days on-treatment (inclusive), as defined in [Section 6.1.6](#)
- For patients with one or more event, the time at risk is the number of days from the start of treatment to the start of the first on-treatment event (inclusive).

The total time at risk (years) for a treatment group is the sum of the individual patient times at risk for that treatment group (days) divided by 365.25. Multiple occurrences of the same event for a particular patient will not be counted as separate events in this summary; a patient will either be considered to have no events of the type being summarised, or to have one or more occurrences of that event.

Additional trial-specific information captured in the eCRF for acute gall bladder disease, acute pancreatitis and thyroid mass will be listed only and not summarised.

A frequency table will be produced of symptoms of injection site reaction (swelling, induration, heat, redness, pain, other) for the subset of patients with the event.

AESIs

Hepatic injury is the only AESI pre-specified in the CTP. No further AESIs have been identified through increasing knowledge of the drug safety profile during the conduct of the trial.

AESIs as recorded by the investigator on the eCRF page will be summarised as part of the overall AE summary, described above.

Investigator-recorded AESIs will also be summarised by treatment, primary SOC and PT.

An additional table will present the frequency of patients with AEs possibly indicating hepatic injury as defined by the four MedDRA subSMQ definitions given below:

- Liver related investigations, signs and symptoms (narrow subSMQ)
- Cholestasis and jaundice of hepatic origin (narrow subSMQ)
- Hepatitis, non-infectious (narrow subSMQ)
- Hepatic failure, fibrosis and cirrhosis and other liver damage-related conditions (narrow subSMQ).

This table will be summarised by treatment, MedDRA subSMQ, primary system organ class and preferred term. Any preferred term which is classified under more than one subSMQ will be included under each relevant subSMQ.

Adjudicated Events

The number and percent of patients with each of the following confirmed adjudicated events (as defined in the CTP) will be presented:

- All-cause death
- Cardiovascular event
- Cerebrovascular disease

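### Most AE tables group patients who stop in escalation by their dose at stopping, which reflects tolerability; only two have a randomised-arm version, and neither covers the escalation period.

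*SAP*

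**What the plan says.** SAP 6.1.3 defines an actual maintenance treatment. For a patient who stops during escalation it is "the next planned maintenance dose up from the last dose which was taken prior to the dose at the time of discontinuation", whatever the reason for stopping. Table 6.1.3:1 lists the result for each pair of dose at stopping and previous dose.

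SAP 7.8 then states: "All safety analyses will be performed on the TS, using actual maintenance treatment". Versions by planned (randomised) treatment are limited to selected AE summaries: "Where this is also planned, it is clearly specified". In SAP 7.8.1 this is specified for two tables, the overall AE summary and all AEs by SOC/PT. In both, the planned version is given as: "Using planned maintenance treatment, with the treatment period pooled across dose escalation and maintenance periods only".

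Four repeats of the SOC/PT table (AEs leading to discontinuation, serious, drug-related, drug-related serious) are produced "using actual maintenance treatment with the treatment period pooled across dose escalation and maintenance periods, only". The worst-intensity table has no planned version stated. Nor does this one: "An exposure-adjusted summary of all AEs by primary SOC and PT will also be produced".

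The disposition table uses planned treatment. It includes this: "The number of patients and reasons for prematurely discontinuing treatment will also be displayed separately for the dose escalation and maintenance periods".

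Protocol 7.2.5 asks for safety by actual maintenance treatment, with key analyses repeated by randomised treatment. It does not say which analyses are key.

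**The concern.** The protocol synopsis makes the escalation scheme and dose range, judged on safety, tolerability and efficacy, part of the primary objective. Protocol 4.1.4 makes intolerance a reason to stop in both the fixed and the flexible escalation phase. A patient in the 4.8 mg arm who cannot tolerate escalation and stops is therefore usually counted under a smaller dose, while arm-mates who tolerate it stay in the 4.8 mg column. The column a patient appears in depends partly on the outcome that the table is meant to compare.

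At stake is the AE detail that bears most directly on tolerability: which events led to stopping, how severe events were, and what happened during escalation. As planned, this detail is not available as a randomised comparison.

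**Working it through.** **Step 1. Reproduce the plan's table.** Inputs: the text rule of SAP 6.1.3, with the previous dose read as the previous dose level, and the maintenance doses 0.6, 2.4, 3.6 and 4.8 mg. Taking the smallest maintenance dose above the previous level reproduces 11 of 11 rows of Table 6.1.3:1. A stop at 0.3 or 0.6 mg counts as 0.6 mg. A stop at 0.9 to 2.4 mg counts as 2.4 mg, at 3.0 to 4.2 mg as 3.6 mg, and at 4.8 mg as 4.8 mg.

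**Step 2. Apply it to the schedules in protocol Table 4.1.4:1.** The cells give the weeks in which a stop is counted at each dose.

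| Randomised arm | as 0.6 mg | as 2.4 mg | as 3.6 mg | as 4.8 mg | weeks counted lower |
|---|---|---|---|---|---|
| 4.8 mg | 1-4 | 5-12 | 13-16 | 17-20 | 16 of 20 |
| 3.6 mg | 1-4 | 5-14 | 15-20 | none | 14 of 20 |
| 2.4 mg | 1-4 | 5-20 | none | none | 4 of 20 |
| 0.6 mg | 1-20 | none | none | none | 0 of 20 |

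No stop enters the 4.8 mg column from another arm. If every flexible step in the 4.8 mg arm is held for three weeks, 19 of 20 weeks map lower. After a week-11 move to the 3.6 mg scheme, all 20 do.

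**Step 3. Count the AE tables.** In SAP 7.8.1 two have a randomised-arm version. Without one are 4 SOC/PT repeats, 1 worst intensity, 3 by body weight, 1 exposure-adjusted, 1 injection site, 1 AESI, 1 hepatic and 1 adjudicated events: 4 + 1 + 3 + 1 + 1 + 1 + 1 + 1 = 13, before the registry disclosure summaries.

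**Step 4. Illustrate the size.** The documents give neither stop rates nor timing, so both are assumed. Take 70 per arm, planned schedules, no maintenance stops, and 25% of the 4.8 mg arm stopping in escalation: x = 0.25 × 70 = 17.5. With a share f of these in weeks 17-20, the 4.8 mg column shows

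f·x / (70 − (1 − f)·x).

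*Hazard proportional to dose.* The weekly doses in the 4.8 mg arm sum to 48.6 mg over 20 weeks and 29.4 mg over the first 16. Patients still on treatment after week 16: 70 × 0.75^(29.4/48.6) = 58.8. After week 20: 70 × 0.75 = 52.5. Stops in weeks 17-20: 58.8 − 52.5 = 6.3. Shown: 6.3/58.8 = 10.7%.

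For the 3.6 mg column, the arm itself has 13.8 stops, of which 7.2 fall in weeks 15-20, and 5.5 arrive from the 4.8 mg arm. Shown: (7.2 + 5.5)/(70 − 13.8 + 12.7) = 12.7/68.8 = 18.4% (the denominator is from unrounded counts).

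*Hazard proportional to dose squared.* The squared weekly doses sum to 172.62, and to 80.46 by week 16. After week 16: 70 × 0.75^(80.46/172.62) = 61.2. Stops in weeks 17-20: 61.2 − 52.5 = 8.7. Shown: 8.7/61.2 = 14.2%. The 3.6 mg column shows 13.5/73.1 = 18.4%.

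| 4.8 mg arm, escalation stops | dose-proportional | dose squared |
|---|---|---|
| 15% by arm | 6.2% | 8.3% |
| 25% by arm | 10.7% | 14.2% |
| 35% by arm | 15.6% | 20.5% |

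Bounds at 25%: 0% if f = 0, and 17.5/70 = 25% (no error) if f = 1.

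**Step 5. Other AEs can move the other way.** Four patients with a serious AE during maintenance at 4.8 mg are 4/70 = 5.7% by arm. On the dose-proportional denominator they are 4/58.8 = 6.8%.

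**Step 6. Week-11 step-down.** Protocol 4.1.4 moves patients of groups B and C who do not tolerate treatment at the week-10 assessment onto the group A scheme, that is from 1.2 to 0.6 mg. Table 6.1.3:1 is presented as covering every dosing possibility in the protocol, but it has no row for 0.6 mg after 1.2 mg. For such a patient who then stops in escalation, the text rule gives 2.4 mg, the next maintenance dose above 1.2 mg. One who continues on 0.6 mg into maintenance is assigned 0.6 mg.

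**The case against.** The strongest reply is that the SAP follows protocol 7.2.5 and already shows the main results by randomised arm. Disposition gives stops and reasons by phase. The overall AE summary by planned treatment has rows for any AE leading to discontinuation, any serious AE, any drug-related AE and any drug-related serious AE. All AEs by SOC/PT are also shown by planned treatment, and safety is descriptive throughout. This stands, and it limits the point to detail and period. The percentages in step 4 show how far the columns shift. They do not measure information that is otherwise unavailable, because total stops by arm are in the disposition table.

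Four stronger readings are tempting but not supported.

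- *That most 4.8 mg escalation stops are moved.* The documents support 16 of 20 weeks, not a share of stops. Under the dose-squared assumption about half stay: 8.7 of 17.5 at 25%, and 5.4 of 10.5 at 15%.
- *That discontinuation by randomised arm is hidden.* It is not, as above. The Kaplan-Meier curves do not name their grouping, but they sit under Disposition. SAP Table 6.3:1 assigns disposition to the screened and randomised sets, and the randomised set is analysed as randomised.
- *That the 4.8 mg dose will look better on every AE.* Early stoppers leave the denominator too, so the direction is not fixed (step 5).
- *That the SAP departs from the protocol.* Two tables by randomised treatment are a defensible reading of an undefined term.

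**Conclusion.** The point holds as a cheap improvement to the safety tables. The reassignment follows directly from SAP Table 6.1.3:1 and protocol Table 4.1.4:1, and needs no assumption beyond the planned schedules. Missing by randomised arm are AEs leading to discontinuation, serious, drug-related and drug-related serious AEs by SOC/PT, worst intensity, exposure-adjusted AEs, and any AE table for the escalation period.

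The size depends on assumed rates and timing. If a quarter of the 4.8 mg arm stops in escalation, its actual-treatment column reads 10.7% or 14.2% under the two hazards tried. It falls below the 3.6 mg column both times, although by randomised arm 4.8 mg has the higher rate (17.5 against 13.8 stops of 70 when the hazard is proportional to dose). If all stops fall in weeks 17-20 there is no distortion. The missing row for 0.6 mg after 1.2 mg is a separate, small gap in the rule.

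**What to change.** Keep the actual-treatment tables, as protocol 7.2.5 requires, and make these changes.

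1. Add planned-treatment versions of the tables for AEs leading to discontinuation, serious, drug-related, drug-related serious, worst-intensity and exposure-adjusted AEs.
2. Add the escalation-period split to the planned-treatment versions of the overall AE summary and the SOC/PT table.
3. State in SAP 7.8 that tolerability comparisons between doses and escalation schemes rest on the randomised versions.
4. Reconcile SAP 6.1.3 and Table 6.1.3:1 with protocol 4.1.4 for patients moved from 1.2 to 0.6 mg at week 11 who then stop during escalation.

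No change is asked for laboratory, vital-sign or ECG tables. The additions reuse planned programs with a grouping variable that the SAP already applies, plus one row or sentence in 6.1.3. The downside is a longer report.

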4.1.4 Drug assignment and administration of doses for each patient

Table 4.1.4:1 Dose Escalation Scheme

| Dose group | Weekly dose in (mg) | | | | | | | | | | | | | | | | | | | |
|-------------------|---|---|-----|---|-----------------|---|-----------------|---|-----------------|----|--|----|-----------------|----|-----------------|----|-----------------|----|-----------------|----|
| | Fixed escalation (titration is not allowed) | | | | | | | | | | Flexible escalation (titration is allowed) | | | | | | | | | |
| Week of treatment | 1 | 2 | 3 | 4 | 5 | 6 | 7 | 8 | 9 | 10 | 11 | 12 | 13 | 14 | 15 | 16 | 17 | 18 | 19 | 20 |
| Escalation | | | 1st | | 2 nd | | 3 rd | | 4 th | | 5 th | | 6 th | | 7 th | | 8 th | | 9 th | |
| BI A | 0.3 | | 0.6 | | 0.6 | | 0.6 | | 0.6 | | 0.6 | | 0.6 | | 0.6 | | 0.6 | | 0.6 | |
| BI B | 0.3 | | 0.6 | | 0.9 | | 1.2 | | 1.2 | | 1.8 | | 1.8 | | 2.4 | | 2.4 | | 2.4 | |
| BI C | 0.3 | | 0.6 | | 0.9 | | 1.2 | | 1.2 | | 1.8 | | 2.4 | | 3.0 | | 3.6 | | 3.6 | |
| BI D | 0.3 | | 0.6 | | 0.9 | | 1.2 | | 1.8 | | 2.4 | | 3.3 | | 4.2 | | 4.8 | | 4.8 | |

Fixed dose escalation phase (week 1- week 10)

During this phase the patient will receive planned dose as described Table 4.1.4:1 and titration within the dose group will not be allowed. Patients who cannot tolerate study drug during this period despite of all the efforts taken, will be discontinued from treatment.

Tolerability assessment after 10 weeks

Tolerability will be assessed after 10 weeks of treatment prior to dosing (visit 7). Patients who cannot tolerate medication in the week after dosing of week 10, will not continue titration to the next step, but will be moved to the next lower dosing available at week 11 and continue with this new scheme for the remaining visits

- Patients of Group D will then follow scheme of group C
- Patients of Group C and B will then follow scheme of group A
- For patients of group A, there is no lower dose possible. They will be maintained with same scheme, and if they again cannot tolerate at next visit they will be discontinued

Flexible dose escalation phase (week 11- week 20)

During this time, the investigator should make every effort to follow every two weeks dose escalation however, adjusting dosing scheme based on the patient tolerability of GI AEs will be allowed, in a blinded manner, as per the below:

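### SAP Table 6.1.3:1 omits the planned step-down from 1.2 mg to 0.6 mg, so a patient who stops after it is grouped at a higher dose than one who continues

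*SAP*

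**What the plan says.** SAP 6.1.3 defines actual maintenance treatment with four rules.

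- A patient who starts maintenance on less than the randomised dose is grouped by what was being taken then: "actual maintenance treatment will be defined as this dose at the start of the maintenance period".
- A patient who stops during escalation is assigned "the next planned maintenance dose up from the last dose which was taken prior to the dose at the time of discontinuation". The SAP says that its table sets this out "for all dosing possibilities planned in the CTP". It also says: "The same rule will be applied irrespective of the reason for discontinuing treatment during the dose escalation period".
- A fallback: "In all other cases, actual maintenance treatment will be defined equal to planned maintenance treatment".
- Placebo patients stay in placebo.

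Table 6.1.3:1 then lists 11 pairs of dose at discontinuation and previous dose. Apart from the first row, which has no previous dose, every row is an upward step.

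Protocol 4.1.4 contains a planned downward step. After the week 10 tolerability assessment, for those who cannot tolerate the medication: "Patients of Group C and B will then follow scheme of group A". In Protocol Table 4.1.4:1, groups B and C receive 1.2 mg in weeks 7-10, and scheme A is 0.6 mg from week 3 onward. The same section foresees discontinuation in weeks 11-20 when intolerance persists.

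SAP 7.8 sets the grouping for safety: "All safety analyses will be performed on the TS, using actual maintenance treatment". Selected AE summaries are repeated by planned treatment.

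**The concern.** The planned path 1.2 mg, then 0.6 mg, then stop has no row in a table that claims to be complete. The prose rule fills the gap with 2.4 mg, a group above anything the patient took and above the 0.6 mg scheme the patient had been moved to. Had the patient stayed on 0.6 mg until maintenance began, the first rule would have assigned 0.6 mg. Stopping earlier on the same dose therefore raises the dose group.

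The patients concerned are selected for intolerance, and the tables that use this grouping describe tolerability by dose. The gap also leaves room for different programming choices on the same data.

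**Working it through.** No sample-size or power formula applies. The check lists every dose pair the protocol can produce in weeks 1-20 and compares each with the SAP.

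**Inputs.** Schemes A to D from Protocol Table 4.1.4:1; the week-11 moves D to C, C to A and B to A from Protocol 4.1.4; maintenance doses 0.6, 2.4, 3.6 and 4.8 mg; the 11 rows of SAP Table 6.1.3:1. The three-week holds allowed in the flexible phase delay steps but do not change the order of doses, so they add no pairs.

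**Step 1: reproduce the SAP table.** Read the prose rule as the smallest maintenance dose strictly above the previous dose level. This returns all 11 rows. Reading it as equal or above fails on three (0.9 after 0.6, 3.0 after 2.4, 3.3 after 2.4), so the strict reading is the one the SAP uses.

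**Step 2: list the reachable pairs.**

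| Dose at stop / previous (mg) | Reached on (weeks) | SAP row | Prose rule |
|---|---|---|---|
| 0.3 / none | all (1-2) | 0.6 | 0.6 |
| 0.6 / 0.3 | A (3-20); B, C, D (3-4) | 0.6 | 0.6 |
| **0.6 / 1.2** | **B to A, C to A (11-20)** | **none** | **2.4** |
| 0.9 / 0.6 | B, C, D (5-6) | 2.4 | 2.4 |
| 1.2 / 0.9 | B, C (7-10); D (7-8) | 2.4 | 2.4 |
| 1.8 / 1.2 | B (11-14); C (11-12); D (9-10); D to C (to 12) | 2.4 | 2.4 |
| 2.4 / 1.8 | B (15-20); C, D to C (13-14); D (11-12) | 2.4 | 2.4 |
| 3.0 / 2.4 | C, D to C (15-16) | 3.6 | 3.6 |
| 3.3 / 2.4 | D (13-14) | 3.6 | 3.6 |
| 3.6 / 3.0 | C, D to C (17-20) | 3.6 | 3.6 |
| 4.2 / 3.3 | D (15-16) | 3.6 | 3.6 |
| 4.8 / 4.2 | D (17-20) | 4.8 | 4.8 |

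Twelve pairs are reachable and 11 are in the table. The D to C move adds no new pair, because D is already at 1.8 mg in weeks 9-10 and C is at 1.8 mg in week 11.

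**Step 3: readings of the missing pair.**

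- Previous level 1.2 mg, strict rule: 2.4 mg.
- Previous injection 0.6 mg (if the patient had more than one on scheme A), strict rule: still 2.4 mg.
- No matching row, so fallback to planned dose: 2.4 mg for group B, 3.6 mg for group C.
- Keyed on the dose at discontinuation: 0.6 mg.
- Same patient still on 0.6 mg when maintenance starts, first rule: 0.6 mg.

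The highest dose taken on this path is 1.2 mg.

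**Step 4: number of patients.** Groups B and C hold 2 × 70 = 140. The documents give no step-down or stopping rate for this path, so both rates are assumptions: affected = 140 × (proportion stepping down) × (proportion of those stopping before week 20).

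- Low: 140 × 0.05 × 0.20 = 1.4
- Middle: 140 × 0.10 × 0.50 = 7.0
- High: 140 × 0.20 × 0.50 = 14.0

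**Step 5: which outputs use the rule.**

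- Affected: safety tables on the Treated Set (SAP 7.8), exposure (SAP 7.7), and the descriptive weight summaries by actual treatment (SAP 7.4). In SAP 7.8.1 the system-organ-class and preferred-term tables of AEs leading to discontinuation, serious AEs and drug-related AEs are specified by actual treatment only.
- Not affected: the primary analysis and MCPMod (SAP 7.4.1) and the disposition table with reasons for stopping treatment (SAP 7), all by planned treatment.

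**The case against.** The best defence is that the rule deliberately assigns doses above those taken. The rows 0.3 with no previous dose, 0.9 after 0.6, 1.2 after 0.9 and 1.8 after 1.2 all do so. A group B patient who stops at 1.2 mg in week 8 is counted under 2.4 mg by design, so counting one who stops just after stepping down from 1.2 mg in the same group has some logic. Moving that patient to 0.6 mg would also show events that arose at 0.9-1.2 mg under a lower dose.

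Much of this stands. A reader might infer that the fault is attribution to a dose never taken; that is a feature of the whole rule, not of this path. What the defence does not explain is the conflict with the first rule. The SAP already counts a stepped-down patient at 0.6 mg, earlier events included, if that patient reaches maintenance. It also leaves the claim of completeness untrue.

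It is also fair that safety is descriptive and that the overall AE summary and the all-AE table are repeated by planned treatment. Those versions avoid the disputed rule, and the overall summary includes total counts of serious AEs, drug-related AEs and AEs leading to discontinuation. They place these patients at 2.4 mg (B) or 3.6 mg (C), however, so they do not show what a consistent actual-treatment grouping would.

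**Conclusion.** The point holds as an inconsistency in one analysis-grouping rule. One of 12 planned dose pairs is missing from a table described as complete. The prose rule sends it to 2.4 mg and the fallback could send group C patients to 3.6 mg, while the same patient continuing into maintenance is counted at 0.6 mg. Under the stated assumptions about 1 to 14 patients are affected; the true number could lie outside that range.

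Three stronger readings are not supported.

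- That treatment discontinuations in general are misreported: the disposition table uses planned treatment, and only the AE tables by actual treatment carry the problem.
- That the 2.4 mg group is inflated by all affected patients: those from group B were randomised to 2.4 mg already, and group B step-downs who continue leave for 0.6 mg, so the net size cannot be fixed from the documents.
- That dose selection is shown to be distorted: the primary dose-response analysis is untouched, and SAP 7.4.1 bases the phase 3 choice on efficacy, tolerability, safety and other information together.

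It should still be corrected, because the affected patients are the intolerant ones and several AE tables have no planned-treatment counterpart.

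**What to change.** Before final database lock, in SAP 6.1.3:

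- Add one row to Table 6.1.3:1: 0.6 mg at discontinuation, previous dose 1.2 mg (step-down to scheme A), actual maintenance treatment 0.6 mg.
- State that the rule taking the next maintenance dose up applies to upward steps only.
- Leave the existing rows in place for D to C patients. Do not add a general rule assigning the maintenance dose of the scheme stepped down to: a D to C patient stopping at 1.8 mg in week 11 would then move from 2.4 mg to 3.6 mg, twice the highest dose taken.

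The cost is one table row, one derivation condition and a revised SAP version. The downside is that events that arose at 0.9-1.2 mg before the step-down will appear under 0.6 mg, as already happens for stepped-down patients who continue into maintenance. A footnote can say so. The change concerns analysis grouping only and takes no position on the dosing rules.
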